### 5.2.5.2 Physical examination

A physical examination including weight

will be performed at screening and at the time points specified in the [flowchart](#). During the physical examination, the patient should be assessed for possible adverse events.

## 5.3 OTHER

### 5.3.1 Other endpoints

Exploratory evaluation of the parameters outlined in [section 5.3.2](#) will be performed in this trial, without being defined as formal endpoints.

Proprietary confidential information.

© 2016 Boehringer Ingelheim International GmbH or one or more of its affiliated companies. All rights reserved.

This document may not - in full or in part - be passed on, reproduced, published or otherwise used without prior written permission.

### **5.3.2 Other assessments**

#### **5.3.2.1 Demographics and history**

Demographics (sex, birth date, race), and baseline conditions will be collected during the screening visit. A detailed cancer history will be obtained. The date of first diagnosis of NHL (month and year may be sufficient) will be recorded in the eCRF. The Ann Arbor stage at diagnosis and at screening should be recorded (see [appendix 10.4](#)). Previously administered chemo- and immunotherapy will be documented, including start and end dates (year and month may be sufficient), the treatment regimen/protocol with the number of courses (chemo-, immunotherapy), the best response obtained (complete remission, partial remission, stable disease, progressive disease, unknown) and the date of progression after each prior therapy (year and month may be sufficient). If the patient has received chemotherapy with autologous or allogeneic stem cell support, procedural details, including the treatment regimen prior to stem cell support should be collected. Documentation of previous radiotherapy should include the total radiation dose and radiation field(s). Previous surgeries within the past five years should be recorded. In addition, any previous surgery, which may affect tumour assessment in this trial according to the investigator, *e.g.* splenectomy or removal of lymph nodes, should be documented in the eCRF.

#### **5.3.2.2 Concomitant diagnoses**

Concomitant diagnoses present at study entry and/or during screening and relevant to the patient's safety during the trial as judged by the investigator will be recorded in the eCRF.

#### **5.4 APPROPRIATENESS OF MEASUREMENTS**

Determination of MTD (or an OBD/recommended dose for further development) is based on toxicities graded according to CTCAE ([R10-4848](#)) The CTCAE criteria are commonly used in the assessment of adverse events in cancer patients. The criteria to be used for evaluation of response are well established ([R04-1585](#)).

## 6. INVESTIGATIONAL PLAN

### 6.1 VISIT SCHEDULE

During the treatment phase, patients are required to be hospitalized under close surveillance with access to intensive care for at least 48 hours after the first dose of BI 836826 to allow close monitoring for infusion-related reactions, tumour lysis syndrome or other adverse events. In case of the split first dose administration patients are required to be hospitalized for at least 72 hours after the start of the low dose of BI 836826. If the first administration of BI 836826 was well tolerated by a patient the investigator may evaluate the risk for an infusion-related reaction and other adverse events in view of relevant comorbidities or disease-related symptoms, and as a result, shorten the duration of surveillance up to 24 hours for the second administration in course 1. If the first 2 infusions of the first treatment course are well tolerated, the 3rd and 4th infusion may be administered on an outpatient basis. For the first treatment of the second course patients need to be hospitalized with surveillance for 24 hours after start of the infusion. If the first infusion of the second treatment course has been well tolerated with limited and easily manageable infusion reactions, the second and subsequent infusions of the second and third treatment course can be administered as an out-patient visit at discretion of the investigator.

In case a visit with administration of BI 836826 is delayed please inform the clinical monitor or the CRA. All subsequent visits with treatment administration will be recalculated based on the actual date of delayed visit. The treatment schedule of weekly infusion should be adhered to, but the visit may be delayed 1-2 days for administrative reasons. To allow for recovery from adverse events or to fulfil the criteria for treatment continuation, delays of more than 2 days are possible as outlined in [section 4.1.4.3](#). If a visit is delayed less than 5 days, the delay may be caught up by shortening the observation period of the course after agreement between investigator and clinical monitor of the trial. Postponement of an infusion for up to 3 weeks can be allowed, but further treatment has to be confirmed by the sponsor. This will be a maximum length of course 1 and 2 to 10 weeks.

In case a patient misses a visit, where there is no planned treatment, the delayed visit should be scheduled as soon as possible and documented with the actual date and the reason for the delayed visit. The next visit, should still take place at the time it was originally scheduled in this treatment course.

### 6.2 DETAILS OF TRIAL PROCEDURES AT SELECTED VISITS

The investigations as outlined in the [flowcharts](#) will be performed at the respective visits as described in detail in the following sections.

#### 6.2.1 Screening and run-in period(s)

The screening period, *i.e.* the phase after informed consent and before the first administration of the trial drug, may be as long as 14 days. However, a pre trial CT scan, performed as part of routine clinical practice, can be used as the baseline CT scan given that the CT scan is

Proprietary confidential information.

© 2016 Boehringer Ingelheim International GmbH or one or more of its affiliated companies. All rights reserved.

This document may not - in full or in part - be passed on, reproduced, published or otherwise used without prior written permission.

valid and encompass neck, thorax, abdomen and pelvis, and it should be performed preferably within 4 weeks before visit 1. If the patient has not received any anti lymphoma treatments and regarded as clinical stable by the investigator, the pre trial CT scan within 8 weeks before visit 1 can be employed. Parameters and investigations according to flowchart for course 1 have to be obtained and / or performed, please refer to [flowchart](#) for Course 1.

## 6.2.2 Treatment periods

The treatment is given in courses with 4 administrations of a weekly infusion followed by observation/rest. Patients can receive up to three courses, *i.e.* 12 administrations. The duration of the first two courses is 7 weeks and for the third course 12 weeks, hence a 3-week or an 8-week observation/rest after the infusions of BI 836826.

### 6.2.2.1 Course 1

In the first course there are 4 visits with treatment and 6 visits for safety assessment. The first two administrations are given as an in-hospital stay for safety, tumour lysis assessment

Between the visits with infusion of BI 836826 safety visits will be performed. After last infusion the safety visits will be weekly. Clinical disease assessment will be performed at the first infusion visit (visit 1) and the last infusion visit (visit 7) as well as the last visit in the course (visit 10).

For details see [flowchart](#) for Course 1.

In case of the split first dose administration patients are required to be hospitalized under close surveillance with access to intensive care for at least 72 hours after the start of the low dose of BI 836826 to allow close monitoring for infusion-related reactions. Please refer the flowchart in [section 10.7](#) for clinical disease, safety

### 6.2.2.2 Course 2

In the second course there are 4 visits with treatment and 6 visits for safety and response assessment. The first administration is given as an in-hospital stay for safety, tumour lysis assessment

Between the visits with infusion of BI 836826 safety visits will be performed. After last infusion the safety visits will be weekly. Clinical disease assessment will be performed at the first infusion visit (visit 1) and the last infusion visit (visit 7). A CT scan of neck, thorax, abdomen and pelvis must be performed at visit 9 to be available for the disease assessment and response evaluation that are planned to be done at the last visit in the course 2 (visit 10).

For details see [flowchart](#) for Course 2.

### 6.2.2.3 Course 3

In the third course there are 4 visits with treatment and 5 visits for safety and response assessment. All infusions can be given as out-patient, if recent previous infusions have been well tolerated. Clinical disease assessment will be performed at the first (visit 1) and at the last infusion (visit 4).

Proprietary confidential information.

© 2016 Boehringer Ingelheim International GmbH or one or more of its affiliated companies. All rights reserved.

This document may not - in full or in part - be passed on, reproduced, published or otherwise used without prior written permission.

CT scan of neck, thorax, abdomen and pelvis will be performed at visit 9 (week 25) unless the EOT visit is performed prior to week 26. Disease assessment, response evaluation with CT scan (see appendix [10.1](#)) will be done at the EOT visit (see below section [6.2.3.1](#)). For details see [flowchart](#) for Course 3.

### 6.2.3 End of treatment and follow-up period

#### 6.2.3.1 End of treatment

The end of treatment (EOT) visit should be performed if patient and investigator refrain from further therapy at any time during the treatment period. For patients who receive course 3 (12 administrations) at the latest 8 weeks after the last administration of BI 836826. If the patient concludes the trial within a treatment course, the information required to be collected at the EOT visit should be obtained as early as possible, preferably immediately. This includes a CT scan, which may be performed if it is considered clinically indicated, *e.g.* to document disease progression. At the EOT visit assessment of all safety and efficacy parameters should be performed according to flowchart for course 3. The status of the patient at EOT has to be documented, *e.g.* in case the patient has progressive disease the date of first documentation of PD has to be recorded. The reason for the completion of active trial treatment or premature discontinuation of trial, if applicable, has to be stated together with date of last administration of the trial drug. If the patient receives other therapy for lymphoma, the therapy has to be stated by name and date of first treatment. For detail see [flowchart](#) for Course 3.

#### 6.2.3.2 Follow-up

Follow-up visits will be performed after the EOT visit in case a patient has completed treatment according to protocol or is not eligible for further treatment courses prior to administration of the maximum number of courses. Follow-up will end in case the patient is

- lost to follow-up
- receives new anti-lymphoma therapy
- withdraws consent
- in case the investigator and sponsor agree not to pursue further follow-up visits
- death

Follow-up visits should be performed at 6 weeks intervals or more frequent if appropriate. Follow-up visits should be done at the investigational site, but may be performed by telephone interview in case the patient is unable to visit the investigator. Follow-up visits should be performed up to 6 months after the end of treatment visit. At the last follow-up visit, an end of trial assessment will be performed and documented in the eCRF. For follow-up of patients with adverse events which have not recovered at the last planned follow-up visit please refer to [section 5.2.2.2](#).

The following will be obtained and / or performed (see [flowchart](#) for Course 3):

- Vital signs (see [section 5.2.5.1](#)), weight, physical examination

Proprietary confidential information.

© 2016 Boehringer Ingelheim International GmbH or one or more of its affiliated companies. All rights reserved.

This document may not - in full or in part - be passed on, reproduced, published or otherwise used without prior written permission.

- Disease assessment: clinical assessment of tumour size (lymph nodes, spleen, liver), imaging if applicable
- Changes in concomitant therapies
- Safety laboratory parameters as specified in [section 5.2.3.1](#)
- Adverse events
- CMV monitoring (see [section 5.2.3.3.2](#))
- Lymphocyte typing (see [section 5.2.3.4](#))
- Status of the patient: date of progression (in case, the patient experienced PD) date death (if applicable)
- Treatment with any other anti-lymphoma drug (report start date of treatment and therapy)

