**Proprietary confidential information.**

**© 2016 Boehringer Ingelheim International GmbH or one or more of its affiliated companies. All rights reserved.**

This document may not - in full or in part - be passed on, reproduced, published or otherwise used without prior written permission.

Clinical disease status will be assessed at screening, at the administration of the first and the last of the 4 infusions and 3 weeks after the last infusion of a respective course with physical examination, clinical assessment of the B-NHL, and blood samples. CT scans in this trial will be performed in accordance with published guidelines for response evaluation in lymphoma ([R04-1585](#)) and correspond to the use in clinical practice ([section 5.1.2.2](#)). A CT scan will be done prior to treatment (may be performed up to 8 weeks (preferably 4 weeks) prior to first infusion), after 2 courses of treatment, (*i.e.* at week 13 +/- window), and just before the end of treatment (EOT) visit (*i.e.* week 25 +/- window). If the CT scans are not possible or available, magnetic resonance imaging can be used instead. However the same imaging methods should be used consistently throughout the trial. Bone marrow examination, PET scan and additional CT scans will be performed at the discretion of the investigator. Results of CT scan, optional PET scan or bone marrow examination performed during the conduct of the trial should be reported in the eCRF. After the EOT visit which may occur at the latest at week 26, the patient will enter the follow-up phase. During the follow-up phase, disease status evaluations (physical examination, clinical assessment of lymphoma, and blood samples) should be performed at least every 6 weeks until 6 months after the EOT visit, administration of new anti-lymphoma therapy or death, whatever occurs first. More frequent visits may be indicated, *e.g.* for follow-up of laboratory parameters or adverse events which have not been resolved at the EOT visit.

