**Proprietary confidential information.**

**© 2016 Boehringer Ingelheim International GmbH or one or more of its affiliated companies. All rights reserved.**

This document may not - in full or in part - be passed on, reproduced, published or otherwise used without prior written permission.

- The patient is no longer able to participate for other reasons (e.g. adverse events unrelated to therapy or disease progression, concomitant diagnoses, pregnancy, surgery or administrative reasons). The investigator may also stop a patient's participation if the patient is unable to attend trial visits

A patient can be withdrawn after discussion between the investigator and the clinical monitor at Boehringer Ingelheim if eligibility criteria are violated and/or the patient fails to comply with the protocol.

All withdrawals will be documented and the reason for withdrawal recorded and discussed, as necessary, in the final report of the trial. As soon as a patient is withdrawn from the trial, the EOT has to be performed if feasible ([see Flowchart for Course 3](#)). Every effort should be made to follow-up patients in case an AE is still ongoing at the time of withdrawal.

Patients who have not completed at least two administrations will be replaced at the same dose level.

Patients who terminate trial treatment due to DLT will not be replaced.

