#### **5.2.2.2 Adverse event and serious adverse event reporting**

Upon inclusion into a trial, the patient’s condition is assessed (*e.g.* documentation of medical history/concomitant diagnoses and diseases), and relevant changes from baseline are noted subsequently.

All adverse events, serious, protocol-specified and non-serious, occurring during the course of the clinical trial (*i.e.*, from signing the informed consent onwards through the observational phase (up to 8 weeks after last drug administration), [table 5.2.2.2:1](#)) will be collected, documented and reported to the sponsor by the investigator on the appropriate eCRFs / SAE reporting forms. Reporting will be done according to the specific definitions and instructions detailed in the ‘Adverse Event Reporting’ section of the Investigator Site File.

For each adverse event, the investigator will provide the onset date, end date, intensity/ CTCAE grading (according to CTCAE, version 4.0, ([R10-4848](#)) treatment required, outcome,

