**Proprietary confidential information.**

**© 2016 Boehringer Ingelheim International GmbH or one or more of its affiliated companies. All rights reserved.**

This document may not - in full or in part - be passed on, reproduced, published or otherwise used without prior written permission.

seriousness, and action taken with the investigational drug. The investigator will determine the relationship of the investigational drug to all AEs as defined in [section 5.2.2.1](#).

All AEs, including those persisting at the End of Treatment (EOT) visit must be followed until recovery or in case of persistence, sufficient characterization has been achieved and the clinical monitor and the investigator agree to not pursue them further.

SAEs and any trial drug related AE grade 3 still ongoing after the end of trial have to be followed until recovery or assessed to be chronic or stable by the investigator.

Table 5.2.2.1 AE/SAE reporting requirements

Time Period	Reporting requirements
From signature of informed consent until 8 weeks after last administration of study drug	Report all AEs, SAEs regardless of relatedness. This includes all deaths.
Post treatment (>8 weeks after last administration of study drug) until end of follow-up (6 months after the end of treatment visit)	Report AEs and SAEs which are considered related to study drug or study design / procedures. Please note: All events leading to death should always be reported as SAE in this trial.
After the individual patient's end of the trial	The Investigator does not need to actively monitor the patient for AEs but should only report relevant SAEs and relevant AESIs of which the Investigator may become aware of.

Patients may be hospitalized during selected phases of the study as required per protocol, *e.g.*, monitoring of trial drug administration, collection of blood for or for administrative reasons. Hospitalizations for administrative reasons and other hospitalizations already planned at the screening visit need not be reported as a SAE in case they are performed “as planned”.

The investigator must report the following events via telephone/fax using the SAE form immediately (within 24 hours or the next business day whichever is shorter) to the sponsor:

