7.8.1.2 Adverse events

AE analysis will be performed for all treatment periods and selected analyses for the MTD evaluation period.

The analyses of AEs will be descriptive in nature and will follow the standard procedure laid down in the Data Management and Statistics Manual (DM & SM) (including all required tables and listings) (current guideline 'Handling and Summarization of AE Data for CTR and Integrated Summaries' (6)). AEs will be coded with the most recent version of Medical Dictionary for Regulatory Activities (MedDRA). The version number will be displayed as a footnote in the respective tables and listings. The SOC will be sorted alphabetically, and PTs will be sorted by descending frequency of adverse events in the "Total" BI 836826 group

Each patient can be observed during the trial under several doses. Analysing the AE of all treatment courses will be carried out under the initial treatment. No formal statistical analysis is planned for the safety comparison.

The analysis of AEs will be based on the concept of treatment emergent AEs. That means that all AEs occurring between the first administration of BI 836826 until 8 weeks after last administration of BI 836826 will be assigned to the on-treatment period. AEs will be distinguished for the treatment course in which the subjects are on-treatment as well as for screening, and post-study. The actual planned dosage of BI 836826 administered on the day each AE starts will also be derived and will be included in the listing. Listings of screening events will not be sorted by initial treatment. Post-study listings will be sorted by initial treatment.

According to the BI standards, multiple recordings of AEs will be collapsed to episodes on the lowest level term and multiple episodes will be condensed to records on the PT and SOC level. CTCAE grade will be an additional criterion for collapsing and condensing AEs. The maximum CTCAE grade will be assigned to episodes and records. CTCAE grade and DLT information will be displayed in AE listings. MedDRA levels for condensing will be SOC and PT.

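### Follow-up ends at new anti-lymphoma therapy with no 8-week minimum, yet all AEs are due, and analysed as on-treatment, to 8 weeks after the last dose

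*Protocol*

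**What the plan says.** **Collection.** Protocol section 5.2.2.2 has all AEs collected from consent "through the observational phase (up to 8 weeks after last drug administration"). The first row of its AE/SAE reporting table covers the period "From signature of informed consent until 8 weeks after last administration of study drug", asks for all events regardless of relatedness, and makes no exception for a next therapy. The middle row runs from 8 weeks to the end of follow-up, given as 6 months after the EOT visit, and asks for related events and for events leading to death. The last row applies once the patient's participation has ended: "The Investigator does not need to actively monitor the patient for AEs but should only report relevant SAEs". It treats AESIs that come to the investigator's attention in the same way.

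**Follow-up.** Section 6.2.3.2 lists the events that end follow-up. One is that the patient "receives new anti-lymphoma therapy"; no minimum time since the last dose is attached. The same section lists adverse events among the items obtained at follow-up, sets visits 6 weeks apart, allows telephone contact, and places an end-of-trial assessment at the last follow-up visit. For a patient who leaves within a course, section 6.2.3.1 wants the EOT information as soon as possible.

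**Analysis.** SAP 7.8.1.2 defines on-treatment events by this rule: "all AEs occurring between the first administration of BI 836826 until 8 weeks after last administration of BI 836826 will be assigned". Protocol 7.3.3 uses the same window. SAP 6.3 uses the Treated Set for all safety analyses, and SAP 7 takes percentages over all patients in the set unless otherwise specified.

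**The concern.** The analysis window and its denominator presuppose that every treated patient is observed for AEs to 8 weeks after the last dose. The visit plan does not secure this for patients who stop early and move to another regimen. Sections 3.3.4.1 and 5.1.2.4 show that a move to next-line therapy is expected.

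Two errors are possible, and they point in opposite directions. If a site takes the end of follow-up as the end of AE collection, events in the rest of the 8 weeks are not actively sought, while the patient stays in the denominator. If a site keeps reporting under the first table row, events that arise under the next regimen enter the tables as BI 836826 on-treatment events. The visible SAP has no cut or flag at the start of new therapy and no exposure-adjusted rate. For efficacy the SAP does deal with new therapy: response uses only assessments before it, and PFS is censored because of it.

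The tables most exposed are all-cause AEs, SAEs and the SAP 7.8.2 count of infections that start within a Grade 4 neutropenia episode. SAP section 3 says the 50 mg and 75 mg Korean cohorts exist because 3 of 4 Korean patients at 100 mg had infections with Grade 4 neutropenia. Those cohorts have 3 to 6 patients each, so one patient is 1/6 = 17% to 1/3 = 33% of a cohort. Later DLT-type events also matter, because protocol 5.2.1.1 and SAP 5.1 use them for the recommended dose.

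**Working it through.** The plan states no figure for this loss, so there is nothing to reproduce. The check is a comparison of rules followed by calendar arithmetic.

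**1. Patients who receive 12 infusions.** The last infusion is on day 22 of course 3 and EOT is on day 77 ± 5 (course 3 flowchart, footnote 12). EOT therefore falls 72 − 22 = 50 to 82 − 22 = 60 days after the last dose, nominally 55, against a window of 8 × 7 = 56 days. These patients are essentially covered.

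**2. Patients who stop early.** EOT is done at once, the next visit is up to 6 weeks later, and new therapy cancels it. A patient who starts new therapy before the first follow-up visit can have no scheduled contact after EOT. Footnote 8 of the course 3 flowchart refers AE assessment during follow-up to sections 5.2.1 and 6.2.3.2. Section 5.2.1 gives no collection window, and 6.2.3.2 holds the stop rule.

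**3. Window observed if collection stops with follow-up.** Let D be the days from first to last dose and w the weeks from last dose to new therapy. The share observed is (D + 7w)/(D + 56). With weekly infusions and 7-week courses, D = 7, 21 and 70 after 2, 4 and 8 infusions. The values of w are assumptions.

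| Infusions | w = 1 | w = 2 | w = 4 | w = 6 |
|---|---|---|---|---|
| 2 (63 days) | 22% | 33% | 56% | 78% |
| 4 (77 days) | 36% | 45% | 64% | 82% |
| 8 (126 days) | 61% | 67% | 78% | 89% |

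Of the post-dose part alone, w = 2 leaves (56 − 14)/56 = 75% unobserved.

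**4. Effect on an incidence, for illustration only.** Assume a true risk of 40% over the 77-day window, a constant hazard, 4 infusions, and no collection after new therapy. Observed risk in an affected patient is 1 − 0.6^share:
- w = 2: 1 − 0.6^(35/77) = 21%
- w = 4: 1 − 0.6^(49/77) = 28%

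If 20% of patients are affected, the cohort figure is 0.8 × 40% + 0.2 × 21% = 36% (w = 2) or 38% (w = 4). If 50% are affected, it is 30% or 34%. This covers only the scenario in which collection stops. Where the site goes on reporting, the error has the opposite sign, and the documents give nothing from which to size it.

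**5. Primary endpoint.** The MTD evaluation period ends 7 days after the second administration (SAP 5.1). In the example of two infusions and new therapy 14 days later, it has already closed.

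**The case against.** Section 5.2.2.2 is the governing AE section. It ties collection to dosing, not to follow-up visits, and nothing in 6.2.3.2 says that duty lapses. This stands: a careful site would keep collecting. But it would do so with no scheduled contact or laboratory sampling, and what it collected would be analysed as BI 836826 on-treatment events.

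Causality assessment must weigh confounding factors such as concomitant medication, and the SAP tabulates related events separately. This mitigates misattribution only in part, because the all-cause AE and SAE tables and the infection-with-neutropenia table do not depend on relatedness.

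Four stronger readings are tempting, and the documents do not support them:

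- *Section 3.2 also ends AE collection.* Its sentence, running "until 6 months after the EOT visit, administration of new anti-lymphoma therapy or death, whatever occurs first", governs disease-status evaluations. The next sentence allows more frequent visits for unresolved AEs.
- *Section 3.3.4.1 limits collection after withdrawal to AEs already present.* The sentence "Every effort should be made to follow-up patients in case an AE is still ongoing at the time of withdrawal" adds an effort; it does not restrict the first table row.
- *The first and last table rows contradict each other.* The overlap is plausible, because the end-of-trial assessment sits at the last follow-up visit. But the rows run in sequence, and no text equates new therapy with the patient's end of trial.
- *Early progressors are under-ascertained, so the safety profile is biased low.* That is one of two outcomes and depends on site practice.

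The site file's reporting instructions, the AE-handling guideline and some SAP sections are not visible. A rule there cannot be excluded.

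**Conclusion.** The gap is real in the current text. Follow-up can end well inside the 8 weeks that section 5.2.2.2 and both analysis plans treat as fully covered, and no visible rule says how AEs are then sought or separated. Neither the direction nor the size of the error can be derived, because the documents do not give the share of patients who start new therapy within 8 weeks, its timing, or site practice. The figures under the working rest on assumed timing, risk and share, and on collection stopping with follow-up. They show what could be lost; they do not estimate a bias.

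A reader might infer that the MTD is compromised. It is largely unaffected, given where its window ends. What is exposed is overall AE, SAE and infection incidence and the later DLT-type events that inform the recommended dose. The change is worth making because it is specific and cheap.

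**What to change.** 1. **Protocol 6.2.3.2.** State that new anti-lymphoma therapy, or stopping treatment, ends disease follow-up, while AE/SAE collection under 5.2.2.2 continues to 8 weeks after the last administration unless consent is withdrawn or the patient dies. Close that period with one contact, by telephone if needed, which the section already permits for follow-up visits.
2. **Reporting table in 5.2.2.2.** Let the last row start no earlier than 8 weeks after the last administration.
3. **SAP 7.8.1.2.** Flag AEs with onset on or after the start of new NHL therapy, and tabulate on-treatment AEs with and without them. The start date is already recorded at EOT and follow-up, so no new data field is needed.

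Section 3.2 needs no substantive change, since its stop is already limited to disease-status evaluations.

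Cost: some protocol wording, one telephone contact for patients who stop early, and one flag with a repeated table. A few extra AE entries after the next therapy starts are to be expected.
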